If he/she indicates that she/he is ready and wants to participate in this research study, she/he will be asked to complete the questionnaires such as socio-demographics and fear of falling.

Procedure for contacting participants for timepoint 2:

Experimental procedures for both groups

We will assess the static balance performance using the BBS. Participants will take off their shoes and stand as still as possible on the balance plate with hands on their hips and eyes closed for 2-3 minutes. Participants will then complete the

dynamic balance performance test using the sit to stand by full standing up from a chair as many as possible within 30 seconds.

Participants will be stratified by the FRA matrix.¹⁷ We will continually evaluate across four groups (rational/ incongruent/ irrational/ congruent) to maintain equal cell distribution (30 OAs/group)*.

- 1) rational FRA: low FOF [Short Fall Efficacy Scale International (short FES-I) score ≤ 10] and aligned with normal balance (BBS score = 0-30).
- 2) incongruent FRA: low FOF (short FES-1 score ≤ 10) despite poor balance (BBS score= 31-100).
- 3) irrational FRA: high FOF (short FES-I score > 10) whereas normal balance (BBS score= 0-30).
- 4) congruent FRA: high FOF(short FES-I score > 10) and poor balance (BBS score= 31-100).¹⁷

**Please note: This is not an intervention study and subjects will not be assigned to the study group.*

They will perform the hand-grip strength and sit to stand tests. Hand-grip strength will be measured in kilograms (kg) as maximal isometric force achieved on a hand-grip dynamometer. This test will be administered with participants sitting in a chair with feet flat on the floor and the elbow bent at 90°. The dynamometer will be placed in the hand and adjusted so the palm side of the grip will be at the palm, and the front end will be lined up between the joints of the medial and distal phalanges. The grip size will be adjusted so that the second metacarpals were flat with a 90° bend at the knuckles. Participants will be asked to squeeze the strength gauge as hard as possible for 3–5 seconds. Three trials on each hand will be performed with 30-s of rest given between trials. Participants will complete the sit to stand by full standing up from a chair as many as possible within 30 seconds.⁷⁸

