13.4 Describe materials that will be used to recruit subjects

We will post an advertisement for participants screening in the form of a flyer on the public boards (in dining rooms, entrances, elevators) and social media. See the printed advertisement.

13.5

All 120 participants are estimated to complete the study, and they will be enrolled in this study for 9 days with two visits. The participants will receive \$30 Walmart gift card after they are done with the second visit. If participants withdraw from the study, they will not receive them. All 60 participants are estimated to complete the second timepoint assessment, and they will be enrolled in this study for 9 days with two visits. The participants will receive \$30 Walmart gift card after they are done with the second visit. If participants withdraw from the study, they will not receive them.

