Specific Aim 2 Sample Size and Power Analysis. There is no historical precedent and limited information to inform the sample size for this study; therefore, the sample size estimate was based on the variable of the BBS score in our pilot study. The standard deviations of the mean BBS scores in our pilot study were 7.91 in the high PA group and 7.78 in the low PA group (PA by self-report), assuming a two-tail alpha 0.05 and a power 0.8, the estimated total sample size N=120 would allow to sufficiently detect a mean difference about 5 between the two groups. Furthermore, to be able to compare the effect sizes of the different body composition and PA measures, we will perform post-hoc analyses to compare the mean values between the two groups of PA, adjusted for the age group.

Aim 3. Determine the dynamic relationships between fall risk appraisal, body composition, physical activity and behavioral changes related to fear of falling

We hypothesize that higher percentage body fat, and lower frequency and duration of physical activity are associated with fall risk appraisal and the associations vary between four groups. We will collect data at the 2nd timepoint and then a dynamic prediction model will be used to investigate their temporal, dynamic associations.

17.2

We will maintain a master list that will contain identifiable data and links the subject ID codes with the participant's information. The electronic version of this master list will be encrypted, password protected, and stored on a computer and is located in a restricted access room at the College of Nursing. The master list is the only document with identifiable data.

All research data, including identifiers and linking sheets, will be retained for at least 5 years after the study closure.

The de-identified data (such as balance performance test data will be password protected, encrypted, and stored on computers and external hard drives in the restricted access laboratory). The de-identified data will be kept indefinitely. The reason for keeping the de-identified data indefinitely is for scientific reproducibility and transparency.

17.3 NA

17.4

Efforts will be made to limit the use and disclosure of participants' personal information, including research study to people who have a need to review this information. We cannot promise complete secrecy.

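### The Aim 2 power statement rests on a two-group BBS comparison with an unstated PA split, and does not cover the planned 30-versus-30 FRA contrasts, which reach 80% power only at about 0.74 SD

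*Combined protocol and SAP*

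**What the plan says.** Section 17.1, under the heading for Aim 2 sample size and power, states that "the sample size estimate was based on the variable of the BBS score in our pilot study". The standard deviations of the "BBS scores in our pilot study were 7.91 in the high PA group and 7.78 in the low PA group", with PA self-reported. Then, "assuming a two-tail alpha 0.05 and a power 0.8", it concludes that "the estimated total sample size N=120 would allow to sufficiently detect a mean difference about 5 between the two groups". The next sentence adds post-hoc analyses to "compare the mean values between the two groups of PA". The paragraph gives no high:low PA split, no allowance for dropout and no multiplicity adjustment. On dropout, section 13.5 says "All 120 participants are estimated to complete the study".

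The Aim 2 analysis, described just before this in section 17.1, is different. Regression or one-way ANOVA compares continuous outcomes such as BMI and steps/day across four FRA groups. The rational group is the reference for the other three. Section 6.4 sets the group sizes: recruitment is monitored "to maintain equal cell distribution (30 OAs/group"). The same section defines the groups by short FES-I score (10 or below versus above 10) and BBS score (0-30 versus 31-100).

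**The concern.** There are two gaps. First, a reader who puts the stated SDs, alpha and power into a standard two-group calculation with equal groups does not get 120 for a difference of 5, and the text does not say which other assumption was used.

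Second, the paragraph is presented as the power analysis for Aim 2, the primary objective in the Study Summary. Its comparison uses all 120 people in two PA groups, with BBS as the outcome. The Aim 2 contrasts use 60 people at a time, 30 against 30, with other outcomes. A reader who takes the paragraph at face value would credit those contrasts with 80% power at about 0.64 SD. A null FRA contrast would then be judged against a smaller detectable effect than the design provides.

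**Working it through.** **Inputs.** From section 17.1: SDs 7.91 (high PA) and 7.78 (low PA), two-sided alpha 0.05, power 0.80, N=120, difference about 5. From section 6.4: FRA cells of 30. The PA split is not stated, so a range is shown.

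**Common SD with equal groups.** √[(7.91² + 7.78²)/2] = 7.845. The implied standardised difference is 5/7.845 = 0.64.

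**Reproducing N for a difference of 5, equal groups.** Normal approximation: n per group = 2 × 7.845² × (1.960 + 0.842)² / 5² = 38.6, so 39 per group and 78 in total. Noncentral t: 39 per group gives just over 79% power and 40 per group gives 80.4%, so 80 in total. Neither is 120.

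**Detectable difference at N=120, equal groups.** Normal approximation: 2.802 × 7.845 × √(2/60) = 4.01. Noncentral t: 4.05. Power for 5 is 93.3%.

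**Unequal PA groups, N=120.** Noncentral t, 80% power, SDs weighted by group size, with the high-PA group as the smaller one:

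| Split | Detectable difference | Power for 5 |
|---|---|---|
| 60/60 | 4.05 | 93% |
| 40/80 | 4.28 | 91% |
| 30/90 | 4.65 | 85% |
| 24/96 | 5.03 | 79.5% |
| 20/100 | 5.40 | 74% |

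Making low PA the smaller group changes these by 0.06 or less (5.08 at 24/96).

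**Other routes to 120 for a difference of 5, equal groups.** One-sided alpha gives 62. Power of 90% gives 104 to 106, and 95% gives 128 to 130. Dropout would have to be 1 − 80/120 = 33%, whereas section 13.5 expects none. Alpha of 0.05/6 gives 120 by the normal approximation, but the plan mentions no such adjustment.

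**The planned FRA contrasts, 30 versus 30, in SD units.**
- Detectable difference at 80% power. Normal approximation: 2.802 × √(2/30) = 0.72 SD. Noncentral t: 0.74 SD.
- Power at 0.64 SD. The noncentrality is 0.637/√(2/30) = 2.47, which gives 68.0% (noncentral t), 69.4% (normal approximation), or 68.7% if the error SD comes from all four cells (116 df).
- With a Bonferroni correction for three contrasts, which the plan does not specify, power at 0.64 SD would be about 51% (noncentral t).

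**The case against.** The strongest reply is that the sentence in section 17.1 is not false. It does not call 120 the minimum, nor does it say that power for 5 is exactly 80%. With equal groups, power for 5 is 93%, so N=120 is more than enough. PA level is observed, not allocated, so equal groups are the reviewer's assumption. The text also says about 5: any smaller-group share from roughly 17% (20/100, 5.40) to 28% (33/87, 4.51) gives a detectable difference that rounds to 5. All of this stands. A reader might infer that the sample size is wrong or that the study is underpowered for the comparison described, and the documents do not support that. What remains is that the split needed to obtain the figure is not reported.

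A second tempting inference is that the FRA contrasts have 68% power for a 5-point BBS difference, or can detect 5.8 BBS points. The documents do not support this either. BBS score helps to define the FRA cells and is not an outcome of those contrasts, and SDs from PA groups do not carry over to cells cut on BBS. The 68% is valid only as power at a standardised difference of 0.64. The plan gives no SD or target difference for PA or body composition, so power for a specific difference in BMI or steps/day cannot be computed.

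The plan is also open that it had little information for sizing. That explains the choice of a surrogate variable. It does not supply a power statement for the FRA contrasts.

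**Conclusion.** The point holds in a limited form. The only justification for N=120 cannot be reproduced from its stated inputs with equal PA groups: these need about 80 people for 5, or give 4.05 at N=120. A figure of about 5.0 requires a split near 1:4 that the plan does not state. For that comparison the discrepancy is on the safe side unless the smaller PA group falls below about 25 of 120.

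The more consequential part is that the paragraph does not describe the planned Aim 2 contrasts. Each has about 68% power at the implied 0.64 SD and reaches 80% only at about 0.74 SD. These figures assume that cells of 30 are achieved with complete data, a common within-cell SD, two-sided 0.05 per contrast, and no multiplicity or covariate adjustment. This is a reporting defect worth correcting and gives no reason to change N.

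**What to change.** Keep N=120 and replace the conclusion of the sample-size paragraph in section 17.1 with wording such as:

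> N=120 detects a BBS difference of about 4.05 with equal PA groups, rising to about 5.0 at a 1:4 split (80% power, two-sided 0.05). Each planned comparison of an FRA cell of 30 with the rational cell of 30 detects about 0.74 SD at 80% power, unadjusted (68% power at 0.64 SD).

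If the authors used a particular PA split or another assumption to arrive at 5, they should state it. The FRA figure should stay in SD units and not be converted to BBS points.

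The cost is wording only, with no change to recruitment, procedures or analysis. The drawback is that the stated figure for the planned contrasts becomes less favourable.

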1.0 Study Summary

Study Title	Technology-based fall risk assessments for older adults in low-income settings
Study Design	We will use a cross-sectional design to address our aims and test hypotheses.
Primary Objective	Examine the associations among fall risk appraisal, body composition, and physical activity.
Secondary Objective(s)	-Examine the feasibility of recruitment (e.g., how many older adults (OAs) need to be screened to recruit the sample?), especially during the COVID-19 pandemic, and acceptability of technologies and procedures for use among OAs in low-income settings. -Determine the dynamic relationships between fall risk appraisal, body composition, physical activity, and behavioral changes related to fear of falling
Research Intervention(s)/ Investigational Agent(s)	NA
IND/IDE #	NA
Study Population	Adults aged 60 years and older
Sample Size	120 participants for timepoint 1 60 participants for timepoint 2
Study Duration for individual participants	Total 9 days with two visits (105-158 mins, total)
Study Specific Abbreviations/ Definitions	Older Adults (OAs) Physical Activity (PA) Fall Risk appraisal (FRA) Fear of Falling (FOF) Assistive Health Technology (AHT) BTrackS Balance Plate (BBP) BTrackS Balance System (BBS) Body Mass Index (BMI) Bioelectrical Impedance Analysis (BIA) Fall-Efficacy Scale International (FES-I) Patient Health Questionnaire-9 (PHQ-9)

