Aim 2 hypotheses are: **1)** Rational FRA is associated with higher levels of PA and skeletal muscle mass, and lower levels of percent of body fat and BMI, **2)** Incongruent FRA is associated with higher levels of PA and skeletal muscle mass, and lower levels of percent of body fat and BMI, **3)** Irrational and congruent FRAs are associated with lower levels of PA and skeletal muscle mass, and higher levels of percent of body fat and BMI. General summary statistics will be presented for continuous data, and percentages will be presented for categorical data. Participant demographic data will be summarized. Analyses will be performed without adjusting for any covariates, followed by the analyses adjusted for age, comorbidities, depressive symptoms, and fall history. Age, the number of comorbidities and the number of falls in the past year will be selected as covariates in the selected model because of their association with FRA, body composition, and PA. Data from InBody770 (e.g., BMI) and ActiGraph (e.g., steps/day) could be modeled as continuous.

Regression models or one-way ANOVA will be used to examine differences in continuous variables (e.g., BMI, steps/day) across the four groups (rational, incongruent, irrational, and congruent FRAs), and categorical variables (e.g., comorbidities) will be tested using Chi-Squared tests. Rational FRA group will set as a base group, and the other three groups (incongruent, irrational, and congruent FRAs) will be compared with this base group. Whenever feasible, models will be adjusted for age, sex, day order, wear time (minutes/day), and the number of fall history. These following variables will add one by one to evaluate the role of each: mobility problems (Y/N), depression (score or category), fall risk (high/low), perceived general health (score of category), medication use (Y/N), and comorbidities (Y/N). A final model will include all significant potential variables to evaluate whether associations between FRA, body composition and PA, whenever feasible.

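### The one explicit comparison of body composition by physical activity level uses two PA groups of unstated source and cut-point, and banded age, although continuous steps/day and age are collected

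*Combined protocol and SAP*

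**What the plan says.** The primary objective in Section 1.0 is "Examine the associations among fall risk appraisal, body composition, and physical activity". One of the three pairs in that objective is body composition with PA.

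The main Aim 2 analysis in Section 17.1 takes body composition and PA as outcomes and compares each across the four fall risk appraisal (FRA) groups. On scale it says "Data from InBody770 (e.g., BMI) and ActiGraph (e.g., steps/day) could be modeled as continuous". Both of its covariate statements list age, not an age group.

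The sample size paragraph that follows then adds, in order to compare effect sizes across body composition and PA measures, that "we will perform post-hoc analyses to compare the mean values between the two groups of PA, adjusted for the age group". It does not say which measure forms the two groups, where the cut falls, what the age bands are, or why grouping is wanted. The two groups mentioned just before are the pilot groups behind the power calculation, with balance score SDs of "7.91 in the high PA group and 7.78 in the low PA group (PA by self-report").

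Section 6.2 describes both an ActiGraph worn for seven consecutive days, which yields steps, and a short self-report PA questionnaire (RAPA).

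**The concern.** A high/low split treats everyone on the same side of the cut as equally active. For a smooth relation this loses precision. It also makes each effect size depend on where the cut falls, which works against an analysis whose stated purpose is to compare effect sizes. Banding age leaves age differences within a band uncontrolled, although age itself is collected and is used in the main models.

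The precision and interpretability of the body composition–PA estimates are at stake. That pair belongs to the primary objective, but none of the Aim 2 hypotheses tests it directly.

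**Working it through.** **Inputs from Section 17.1.** "assuming a two-tail alpha 0.05 and a power 0.8"; SDs 7.91 and 7.78; "the estimated total sample size N=120 would allow to sufficiently detect a mean difference about 5 between the two groups". Section 13.5 assumes no dropout ("All 120 participants are estimated to complete the study"). The allocation between PA groups is not stated; 1:1 is assumed unless noted.

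**The plan's own figure.**
- Pooled SD = √[(7.91² + 7.78²)/2] = 7.845, so d = 5/7.845 = 0.637.
- A two-sided 0.05 test with 80% power needs 78 in total by the normal approximation, or 80 by the t-test. N = 120 is therefore not reproduced at 1:1.
- With 60 per group, power for a difference of 5 is 93.3% (t-test). Power falls to about 80% (79.7%) only if the groups are split about 4:1.
- This mismatch is a separate matter. Here it supplies only the reference value d = 0.637.

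**Information kept by a two-group split.** For a normal measure cut so that a proportion p lies below c, with a linear relation, relative efficiency = φ(c)²/[p(1 − p)].

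| Split | Efficiency | Loss | 120 works like |
|---|---|---|---|
| 50:50 | 0.637 (= 2/π) | 36% | 76 |
| 2:1 | 0.595 | 41% | 71 |
| 75:25 | 0.539 | 46% | 65 |
| 80:20 | 0.490 | 51% | 59 |

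For log-normal steps with a relation linear on the raw scale, a median split loses 41% to 58% as the log-SD goes from 0.3 to 0.7. These log-SDs are assumed; the documents give no distribution for steps.

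**Power at N = 120, median split of a normal measure.** For a correlation r, power = Φ(atanh(r)·√117 − 1.96). The split shrinks r by √(2/π) = 0.798.

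- *Assumed r = 0.253.* Continuous: atanh = 0.2586, times 10.817 = 2.797, power Φ(0.837) = 80%. Split: r = 0.202, atanh = 0.2047, product 2.214, power Φ(0.254) = 60%. A simulation of 20,000 replicates gave 80.1% and 60.4%.
- *The plan's d = 0.637.* Point-biserial r = d/√(d² + 4) = 0.304, so the underlying r = 0.304/0.798 = 0.381. Continuous: atanh = 0.401, product 4.334, power Φ(2.374) = 99%. Two groups: 93%, as above.
- *Smallest correlation detectable with 80% power.* 0.253 continuous; 0.253/0.798 = 0.32 when split.

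**Where the split does better.** Suppose the true relation is a pure step at the median with d = 0.637. The two-group test keeps 93%. A straight line in continuous PA then has r = 0.304 × 0.798 = 0.242, product 2.674, power Φ(0.714) = 76%.

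**Age.** The loss from banding cannot be computed, because the bands are not stated.

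**The case against.** The strongest reply is that the documents never say steps/day is what is cut. The pilot groups were self-reported, and a self-report instrument is collected again. The sentence also aims to compare PA measures between the groups, which would be circular if steps/day defined them. Self-report is thus at least as plausible a source. This stands: the 36% figure is conditional. Under the other reading the objective continuous measure is simply not used as the PA variable in this comparison, and the same remedy applies.

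A reader might infer that this is the only analysis relating PA to the other constructs. The documents do not support that. Section 17.1 also analyses steps/day across FRA groups, announces a final model for FRA, body composition and PA, and plans a dynamic prediction model for Aim 3. The final model has no stated outcome and is conditional on feasibility, and the Aim 3 model concerns change between timepoints. Neither specifies a body composition–PA comparison, but both are stated and neither dichotomises PA.

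A reader might also extend the point to balance. The quoted sentence concerns body composition and PA measures; the balance score by PA group appears only as the basis for the sample size.

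Finally, the analysis is labelled post-hoc, and at the plan's own d both approaches exceed 80% power. Both points are correct and limit the weight of the concern.

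**Conclusion.** The point holds in a limited, conditional form. The one explicit comparison of body composition by PA level rests on two undefined PA groups and banded age, without a reason and in contrast to the approach earlier in the same section.

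If steps/day is split, the loss is about 36% at best, assuming a normal measure, a median cut and a linear relation; it is larger for uneven cuts or for the skewed distributions tried. The power cost ranges from 6 points (93% against 99%) at d = 0.64 to about 20 points (60% against 80%) at r = 0.253. The first effect is borrowed from the balance score and the second is assumed, since the documents give none for body composition. The tests of H2.1 to H2.3 use continuous outcomes across FRA groups and are not affected. This is an inexpensive improvement to a secondary analysis, not a flaw in the main one.

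**What to change.** Replace the two-group comparison with a regression or partial correlation between each body composition measure and continuous ActiGraph mean steps/day, transformed if skewed and adjusted for age in years. Report standardised coefficients with 95% confidence intervals, so that the measures can be compared on one scale, and add a linearity check such as a quadratic or spline term. A partial correlation imposes no direction, which suits the framework in Section 6.1, where body composition precedes FRA and PA follows it.

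Keep the high/low PA means as a descriptive table only, with the source of the groups and the cut-point stated.

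The cost is a few sentences of analysis text, with no new data or participants. The drawback is the assumption of a roughly smooth relation: under a pure step at the cut the linear analysis would lose power, as shown above. The linearity check and the retained table are there to reveal that case.
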